The medical research council (MRC) provided a document in 2000, the MRC model, to help researchers use the correct research designs, methods and measuring instruments (6). This model was revised in 2021 and forms the basis of the design of this project (6). This model structures the analysis using psychometric properties such as: acceptability, adoption, appropriateness, costs, feasibility, fidelity, penetration and sustainability (7).

Primary endpoints

Evaluation of the implementation of a continuous monitoring method on the surgical ward

- Fidelity: The usability and degree of implementation of the Healthdot at the surgical ward. Measured with the System usability scale (SUS), Score > 68 at M6 (8)
- Acceptability: The workload regarding the amount of spot checks in addition to the standard monitoring. Calculated with data from the electronic patient file records.
 Success in case of average reduction of 20% at M6 compared to M3

Secondary endpoints

- Adoption: The intention and attitude towards the use of the Healthdot monitoring method. Measured with evidence-based practise attitude scale (EBPAS)(9, 10).
- Feasibility: The extent to which the Healthdot monitoring method can be successfully carried out by the healthcare employees. Measured with a thematic analysis and input from the core group (Braun and Clark)(11)
- Acceptability: The workload regarding the amount of spot checks per hospital admission day per patient. Calculated with data from the electronic patient file records.
- Acceptability: The perception among nursing staff given the satisfactory and agreeableness regarding workload. Measured with the integrated workload scale (IWS) (12, 13).
- Appropriateness: Relation between device false alarms (noise) and correct alarms based on the alarming protocol. Measured as signal to noise ratio (SNR)
- Appropriateness: Number of unexpected events that occur during or result from the use of the Healthdot medical device. Measured as adverse device events (ADE)
- Feasibility: The amount of time needed to perform and process a complete manual spot check or digital monitoring check. Measured by manual time measurement.
- Costs: Cost-effectiveness analysis based on the duration of admission, the associated admission costs and the monitoring method. Calculation based on provided care and associated costs
- Algorithm improvement: Advanced algorithm analyses for improved monitoring protocols with use of artificial intelligence (AI)

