4. PROJECT POPULATION

a. Population (base)

Around 10 nurses and 5 physicians, working at the designated surgical ward, will sign informed consent and participate as the primary research population in the core group for in depth analysis regarding the implementation evaluation.

Adults, male or female above 18 years old, admitted to one surgical ward at the Catharina hospital will be included in this prospective cohort study. Admission will mainly concern postoperative patients, but readmissions, clinical observation, treatment of complications or transfers from other departments or the intensive care unit are also reasons for admission. Most of the patients that will be treated at this department receive care of oncological surgical nature, but also general surgical patients, urological and gynaecological patients can be admitted to this department.

This ward has an average annual turnover of approximately 900-1000 patients each year based on the previous three years. A study period of 6 months is proposed to obtain a total of 500 patients in total, 250 patients during each study phase.

b. Inclusion criteria

Nurses and physicians are the primary research population for answering the research objectives.

Nurses and physicians, participating in het focus group will sign informed consent. Nurses working at the surgical ward who will fill in the IWS questionnaire at multiple occasions will sign for informed consent on this questionnaire form (attachment 3) for use of the anonymized data.

Patients won't be included for participation since the Healthdot will be the new standard of care regarding monitoring. Patients will however sign informed consent at admission for use of anonymized data.

Core/focus group

Nurses

- Registered in the national register of medical professions (Big register)
- Appointed as a nurse at the Catharina hospital and working in the surgical department during the study period.
- Willingness to participate in the core group for evaluation of the implementation

Physicians

- Registered in the national register of medical professions (Big register)
- Appointed at the Catharina hospital as a physician or resident.
- Willingness to participate in the core group for evaluation of the implementation

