7. METHODS

a. Study parameters/endpoints

i. Main study parameter/endpoint

Primary parameters and endpoints

Evaluation of the implementation of a continuous monitoring method on the surgical ward

- Fidelity: The usability and degree of implementation of the Healthdot at the surgical ward
 - Measured with the System usability scale (SUS), Score > 68 at M6 (8, 26)

- Acceptability: The workload regarding the amount of spot checks in addition to the standard monitoring.
 - Calculated with data from the electronic patient file records. Success in case of average reduction of 20% at M6 compared to M3

ii. Secondary study parameters/endpoints (if applicable)

Secondary parameter and endpoints

- Adoption: The intention and attitude towards the use of the Healthdot monitoring method.
 - Measured with evidence-based practise attitude scale (EBPAS) (9, 10).
- Feasibility: The extent to which the Healthdot monitoring method can be successfully carried out by the healthcare employees.
 - Measured with a thematic analysis (Braun and Clark) with core group (11).
- Acceptability: Amount of manual spot checks per hospital admission day per patient
 - \circ Calculated with data from the electronic patient file records.
- Acceptability: The perception among nursing staff given the satisfactory and agreeableness regarding workload.
 - Measured with the integrated workload scale (IWS) (12, 13).
- Appropriateness: Relation between device false alarms (noise) and correct alarms based on the alarming protocol.
 - Measured as signal to noise ratio (SNR)
- Appropriateness: Number of unexpected events that occur during or result from the use of the Healthdot medical device. Measured as adverse device events (ADE)
- Feasibility: The amount of time needed to perform and process a complete manual spot check or digital monitoring check. Measured manually.
- Costs: Cost-effectiveness analysis based on the duration of admission, the associated admission costs and the monitoring method
- Advanced algorithm analyses for improved monitoring protocols with advanced AI software

iii. Other study parameters (if applicable)

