Additional anonymized data will, in case of informed consent, be collected from the electronic patient file such age, gender, reason for admission, medical history, duration of admission, complications and laboratory results. This additional data will be used to relate the primary and secondary results to any influencing factors/ baseline characteristics and potentially correct for these factors.

Variables eCRF

Characteristic	Input
Indication	Open
Type of invasive interventions/surgery	Open
Gender	M/F
Age	Open
BMI	Kg/m2
Comorbidities	
Charlson comorbidity index	Charlson Comorbidity Index (CCI) - MDCalc
Hospital stay	
Admission date	D/M/Y
Discharge date	D/M/Y
Elective or emergency	Open
Complications	
Clavien-Dindo classification	Grade I-V
Complications type	Cardiac, Pulmonary, Kidney failure,
	infectious, traumatic, surgical related
	(perforation, leakage, bleeding)
Urgent consultations (SIT) during	0-99
hospitalization	
ICU admission	Yes/no
Mortality <30 days	Yes/no
Re-admission < 30 days	Yes/no
Fidelity	
Total minutes monitored	Min
Amount of heart rate measurements	Total number per admission
Amount of respiratory rate measurements	Total number per admission
Artefact heart rate measurements	Total number per admission
Artefact respiratory rate measurements	Total number per admission
Total amount of spot checks	Total number per admission
Device	
Premature removal of device	Yes/no
Replacement of device	Yes/no
Bijzonderheden device	Yes/no

b. Randomisation, blinding and treatment allocation

N/A

c. Project procedures

Prior to the start of the pre-implementation phase there will be a pre-implementation phase during months 1-2. This phase will consist of training the medical staff through e-learning and physical meetings. During this phase, medical staff will have the opportunity to apply the Healthdot, learn to activate it and practise with the Guardian dashboard. This phase serves as preparation for the implementation and aims to optimize the intra-structure in advance. In addition, during this phase, baseline data will be collected about the standard spot check measurements, feeling of confidence and attitude towards a change in the monitoring method. This study is a quality project and a change in standard of care. Nurses and physicians voluntarily participating in the focus group will sign informed consent for participation. Nurses not participating in the focus group but working at the surgical ward during this project will

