8. STATISTICAL ANALYSIS

The statistical analysis at professional (nurses/ physicians) level will be performed by means of descriptive statistics. Each continuous parameter is analyzed for normality by the Shapiro-Wilk test and visually by a figure. Normality-based reporting will be done using medians and interquartile ranges (IQR) or means and standard deviations (SD). Frequencies and percentages are reported for categorical data. Each continuous parameter is checked for normality by the Shapiro-Wilk test and visually by a figure. Normality-based reporting will be a figure. Normality-based reporting is performed using medians and interquartile ranges (IQR) or means and standard deviations (SD).

All analysis are performed using IBM SPSS Statistics 26.0 for Windows (IBM Armork, New York, USA) with 95% confidence interval and p < .05 as statistically significant.

The core group consisting of nurses, physicians and investigators will conduct a structured analysis into the fidelity, feasibility and acceptance of the implementation and this information is processed and objectified by means of a Braun and Clarke thematic analysis.

Objective	Instrument	Variable	Statistical test
Fidelity	SUS ^p	Continuous	Unpaired T-test/ Mann- Whitney U test
Acceptance	SC/day ^p SC/patient ^s IWS ^s	Continuous Continuous Ordinal	Descriptive statistics Descriptive statistics One-way ANOVA test
Adoption	EBPAS ^s	Continuous	Repeated measures ANOVA
Appropriateness	SNR ^s ADE ^s	Continuous Continuous	Descriptive statistics Descriptive statistics
Feasibility	Thematic analysis ^s	Nominal	Braun & Clarke thematic analysis
Time efficiency	Time measurement	Continuous	Descriptive statistics
Costs	Evaluation	Continuous	Descriptive statistics

Table 4: psychometric properties and statistical analysis

a. Other study parameters

N/A

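### The two-sample test that Table 4 assigns to the primary SUS endpoint does not involve 68, so it cannot evaluate the criterion of SUS > 68 at month 6, and the groups compared are not named

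*Combined protocol and SAP*

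**What the plan says.** Section 7.a.i defines the primary fidelity endpoint as "Measured with the System usability scale (SUS), Score > 68 at M6 (8, 26"), and the Summary gives the same threshold. The measurement timetable in section 3 schedules the SUS at months 4 and 6.

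In section 8, Table 4 marks the SUS as primary and continuous. Its method is "Unpaired T-test" or Mann-Whitney U. The table gives no reference value and does not say which two groups are compared.

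Two general statements in section 8 also bear on this endpoint:

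- The section opens with "The statistical analysis at professional (nurses/ physicians) level will be performed by means of descriptive statistics", with mean and SD or median and IQR chosen by normality.
- All analyses are to be done "with 95% confidence interval and p < .05 as statistically significant". This is not linked to the M6 score or to 68.

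On respondents, section 4.a describes the core group as "Around 10 nurses and 5 physicians, working at the designated surgical ward", and section 8 refers to "The core group consisting of nurses, physicians and investigators". The readable text does not say who completes the SUS. The sentence in section 7.c beginning "Nurses not participating in the focus group but working at the surgical ward during this project will" breaks off in the copy reviewed, so this is not treated as an omission.

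**The concern.** The criterion compares one group at one time with a fixed number. The assigned test asks whether two independent groups differ from each other. These are different questions, and a result on one does not settle the other.

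A reader of the results would see a p-value beside a primary endpoint and could take it as bearing on whether usability reached the benchmark, which it does not. A significant result could accompany a missed benchmark, and a non-significant one could accompany a benchmark that was met. The quantity that does bear on the criterion, the M6 score with its interval set against 68, is not assigned to the SUS row.

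Because the groups are unnamed, the comparison is also not prespecified. Month 4 against month 6 is the likelier reading given the timetable, but nurses against physicians is possible.

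**Working it through.** The documents give no SD, expected score or sample size for the SUS, so there is no planned figure to reproduce. The check is one of logic, with illustrative numbers.

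**Inputs.** From the documents: the benchmark of 68, SUS at months 4 and 6, and about 10 nurses and 5 physicians. Assumed: SD 10 to 20, about 15 respondents, and the means below.

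**1. The statistic does not contain 68.** For two groups, t = (mean B − mean A) / (SD × √(1/nA + 1/nB)). Adding any constant to both means leaves t unchanged, so the test cannot register where the scores lie relative to 68. The Mann-Whitney U test uses only the relative ranks of the two groups, so the same holds.

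**2. Reading A: month 4 v month 6, n = 15 each.** Take 52 to 66 (misses 68) and 62 to 76 (meets 68). The difference is 14 in both cases, with 28 degrees of freedom.

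| Assumed SD | Standard error = SD × √(2/15) | t = 14/SE | p, both cases |
|---|---|---|---|
| 10 | 3.65 | 3.83 | 0.0007 |
| 12.5 | 4.56 | 3.07 | 0.005 |
| 20 | 7.30 | 1.92 | 0.065 |

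Test and benchmark can also point in opposite directions. At SD 15, SE = 15 × √(2/15) = 5.48.

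- 50 to 64: t = 14/5.48 = 2.56, p = 0.016, yet 64 misses the benchmark.
- 72 to 78: t = 6/5.48 = 1.10, p = 0.28, yet 78 meets it.

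**3. Reading B: 10 nurses v 5 physicians, SD 12.5.** SE = 12.5 × √(1/10 + 1/5) = 6.85.

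- 66 v 58: overall mean (660 + 290)/15 = 63.3, below 68.
- 78 v 70: overall mean (780 + 350)/15 = 75.3, above 68.
- Both have t = 8/6.85 = 1.17 on 13 degrees of freedom, p = 0.26.

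**4. What would inform the criterion.** This is the M6 mean ± t(n−1, 0.975) × SD/√n. At n = 15 and SD 12.5 the half-width is 2.145 × 12.5/√15 = 6.9. A mean of 66 then has a 95% CI of 59.1 to 72.9, and a mean of 76 has 69.1 to 82.9. Half-widths for other respondent numbers:

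| n | SD 10 | SD 20 |
|---|---|---|
| 12 | 6.4 | 12.7 |
| 15 | 5.5 | 11.1 |
| 18 (three investigators also answer; assumed) | 5.0 | 9.9 |
| 30 | 3.7 | 7.5 |

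**5. Only if the same 15 people answer at both months.** With SD 12.5 and an assumed correlation of 0.5 (200,000 simulated samples), power for an 8-point change is 36% unpaired against 64% paired. The unpaired type I error is 0.8% instead of 5%. In that case the unpaired test is conservative and loses power.

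**The case against.** The strongest reply is that SUS > 68 is a benchmark and no section asks for a hypothesis test of it. Section 8 promises descriptive reporting of each continuous parameter, so the M6 score will be available to set against 68. The other primary endpoint, spot checks per day, has a numerical success rule and is analysed only descriptively. The Table 4 entry could therefore be an extra month 4 to month 6 comparison that is merely under-labelled. This is also a single-ward quality project with no sample-size basis, and nothing makes the SUS p-value the success rule.

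Much of this stands. The endpoint is assessable, and the plan does not force a wrong success verdict. It is also fair that the numerical illustrations rest on assumed values, that the pairing point depends on who answers and whether forms can be linked, and that imprecision at small n is separate from the choice of test.

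It does not remove the mismatch. Table 4 gives the SUS row a test rather than descriptive statistics, which is what it gives the other primary endpoint. Nothing in the plan labels that test as additional or names its groups. The general confidence-interval statement is not attached to the M6 score or to 68.

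**Conclusion.** The concern holds and should be fixed. The method assigned to a primary endpoint answers a different question from its stated criterion, whichever two groups were meant. That conclusion follows from the form of the test and needs no assumed SD or respondent number.

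The consequence is limited. The benchmark can still be read from the M6 summary, so what is at risk is the interpretation and prespecification of the SUS result, not the ability to assess the endpoint. The p-values and interval widths above illustrate size only, under assumed SDs of 10 to 20 and about 15 respondents. The loss of power applies only if the same people respond twice, and the conclusion does not depend on it.

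**What to change.** In the SUS row of Table 4, replace the two-sample test with the M6 SUS mean (or median) and its 95% CI, reported against 68. If a test is wanted, use a one-sample t-test or Wilcoxon signed-rank test against 68. Keep > 68 as the benchmark and report the interval beside it. Section 8's normality rule leaves the choice of mean or median to the data, so it would help to state in advance which one is set against 68.

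Label any month 4 to month 6 comparison as supportive: paired if respondents can be linked, otherwise each month with its own 95% CI. If nurses against physicians was intended, name it and label it supportive. If the full text does not already say who completes the SUS, add one sentence.

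The cost is one table row and an amendment handled under section 9.c. The benchmark, schedule and questionnaire do not change. Linking forms is needed only for a paired comparison. The drawback is a visibly wide interval. At n = 15 an observed M6 mean of 70 meets the benchmark, but its 95% CI would be 64.5 to 75.5 at an assumed SD of 10, widening to 58.9 to 81.1 at an assumed SD of 20.

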We hypothesize that the implementation of het Healthdot will be accepted and supported by the nursing staff and physicians since previous research has generated a positive attitude towards the use of the Healthdot in our hospital. Our assumption is that the attitude towards this change will shift towards an even more positive mindset during the implementation phase and that the training prior to this will have an important contribution. This change will be measured by the questionnaires, calculations and the Braun and Clarke thematic analysis. The device performance and signal-to-noise ratio and adverse device events will be analysed and are not expected to adversely affect the workability based on previous research.

These hypotheses will be accepted or rejected based on the outcome of this clinical investigation.

3. Project DESIGN

This project is designed as a 6-month monocentric prospective cohort at the Catharina hospital in the Netherlands. In the presently unlikely event that other sites will be included during the conduct of het study, amendments will be submitted to all respective internal and external approvers (ICBE, METC). Every patient admitted to the one surgery department during the duration of the study will receive a Healthdot as monitoring device. Implementation of the Healthdot as the new standard of care regarding monitoring will be performed stepwise in different phases: pre-condition phase, pre-implementation phase, implementation phase and maintenance and evolution.

During phase 1 (month 1-3) patients will receive the current standard monitoring method with manual spot checks and EWS. During this phase all healthcare staff involved will receive appropriate training regarding application of the device, reading and assessing the data and protocol explanation to optimize the infrastructure before implementation.

During phase 2 (month 4-6) patients will be monitored with the Healthdot primarily and receive additional manual spot checks if indicated. After these 6 months, the implementation will be evaluated and optimized and potentially extended.

[figure not shown]

Figure 1: Flowchart project design

Surgical	Month 1	Month 2	Month 3	Month 4	Month 5	Month 6
war	Spot check +	Spot check +	Spot check +	Healthdot	Healthdot	Healthdot
d	EWS	EWS	EWS			
Focus	Training	Training	Training	Implementation	Implementation	Implementation
	Infrastructure	Infrastructure	Infrastructure	Evaluation	Evaluation	Evaluation

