	Baseline data	Baseline data	Baseline data	Study data	Study data	Study data

Table 1: Overview focus during project phases

Objective	Instrument	0	1	2	3	4 (Switch)	5	6
Fidelity	SUS ^p					Q		Q
Acceptance	SC/day ^p				AD			AD
	SC/patient ^s				AD			AD
	IWS ^s	Q	Q	Q	Q	Q	Q	Q
Adoption	EBPAS ^s	Q			Q (9- 15)			Q
Appropriateness	SNR ^s							AD
	ADE ^s							AD
Feasibility	Thematic analysis ^s				FG		FG	FG
Time efficiency	Time measurement		М	М	М	Μ	Μ	М
Costs	Evaluation							AD

Q = questionnaire, AD = administered data, FG = focusgroep, M = manual measurement Table 2: Measurement timetable for psychometric properties

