Nursing team working at this surgical ward will fill in the IWS on a weekly base. Every nurse will consent to the voluntary participation for this one question inquiry and consent to use of the anonymous data. No additional informed consent will be asked to this group.

c. Exclusion criteria

Core/focus group

Nurses & Physicians

- Termination of employment within the study period
- Not willingness to participate in the core group

d. Sample size calculation

Sample size calculation is not applicable for implementation projects. Nevertheless, we expect to obtain data from at least 500 patients, 250 patients during each phase, based on the average annual turnover of approximately 900-1000 patients each year over the previous three years at this ward. Our core group contains out of 10 nurses and 5 physicians.

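### One-way ANOVA for the repeated IWS workload ratings ignores that the same nurses rate again and again, so its false-positive rate can depart from 5% in either direction

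*Combined protocol and SAP*

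**What the plan says.** IWS is a secondary endpoint in section 7.a.ii: "The perception among nursing staff given the satisfactory and agreeableness regarding workload". Table 4 in section 8 labels it ordinal and assigns it "One-way ANOVA test"; the same section sets significance at p < .05. The next row, for EBPAS, names "Repeated measures ANOVA". Yet section 8 opens with: "The statistical analysis at professional (nurses/ physicians) level will be performed by means of descriptive statistics".

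The ratings are repeated. Section 4.b speaks of nurses who "fill in the IWS questionnaire at multiple occasions will sign for informed consent on this questionnaire form", and then states: "Nursing team working at this surgical ward will fill in the IWS on a weekly base". The timetable in section 3 ("Table 2: Measurement timetable for psychometric properties") marks an IWS questionnaire in each of the seven columns, months 0 to 6. Section 9.b also relies on repeated IWS measurements for monitoring.

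Table 4 does not say whether the groups are weeks, months or phases, or whether all weekly ratings or one per month enter. No nurse effect or other allowance for repeated ratings is described. Section 4.b and the IWS form in section 11 refer to anonymous use of the data, and no step links one nurse's ratings over time.

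**The concern.** One-way ANOVA judges differences between groups against the spread of ratings within groups, as if each rating came from a different person. Here the same nurses contribute to every group. Two effects follow, and they work against each other:

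- A stable tendency of a nurse to rate high or low adds to the spread within each month but cancels between months. The test becomes too cautious and may miss a real change.
- If several ratings by one nurse in the same month resemble each other more than her ratings in other months, the month means vary more than the test allows for. It may then declare a change by chance.

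At stake is the p-value for the plan's measure of nurses' perceived workload. The primary hypothesis in section 2 expects a benefit on workload, and section 9.g plans publication.

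**Working it through.** **Inputs from the documents:** one-way ANOVA and p < .05 (section 8); weekly completion (section 4.b); seven monthly columns (section 3, Table 2); phases of months 1–3 and 4–6 (section 3). No number of IWS raters, correlation, effect size or power is given, so there is no figure of the plan's own to reproduce.

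**Assumed:** 20 nurses, scores rounded to the 1–9 scale, no true change unless stated, stable staff, and the correlations below. With independent ratings the simulated test rejected in 4.8–5.0%, so the method is calibrated.

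**Step 1: one rating per nurse per month, tested by month.** Let ρ be a constant within-nurse correlation and the total variance 1. The nurse effect cancels between months, so E(MS between) = 1 − ρ, while E(MS within) = 1. The F ratio centres on 1 − ρ, not 1: 0.7, 0.5 and 0.3 at ρ = 0.3, 0.5 and 0.7. Simulated false-positive rates are 0.9%, 0.1% and 0.0%.

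**Step 2: four weekly ratings pooled by month.** Let s be the share of variance from a constant nurse effect and m the share from a nurse-by-month effect. Then E(MS between) = 4m + (1 − s − m) = 1 − s + 3m, and E(MS within) is close to 1.

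| s | m | 1 − s + 3m | Simulated rate |
|---|---|---|---|
| 0.3 | 0 | 0.7 | 1.1% |
| 0.3 | 0.1 | 1.0 | 5.3% |
| 0.3 | 0.2 | 1.3 | 14.1% |

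The direction turns on whether 3m exceeds s, and the two can offset each other almost exactly.

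**Step 3: weekly ratings with AR(1) correlation 0.3/0.5/0.7/0.9 over 24 weeks.**

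| Grouping | False-positive rate |
|---|---|
| By month | 19/32/40/29% (repeat runs: 19–41%) |
| By phase | 13/21/31/35% |
| By week | 4.8/5.6/5.8/2.5% |

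The grouping factor alone, which Table 4 does not name, moves the result from near 5% to 40%.

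**Step 4: power for a 0.5 SD fall in months 4–6, one rating per month, constant ρ.**

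| Test | ρ = 0.3 | ρ = 0.5 | ρ = 0.7 |
|---|---|---|---|
| One-way, by month | 43% | 35% | 26% |
| One-way, by phase | 79% | 84% | 88% |
| Paired t, by phase | 85% | 94% | 99% |

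Repeat runs differ by about a point. Ignoring the pairing costs 85 − 79 = 6, 94 − 84 = 10 and 99 − 88 = 11 points. Moving from the monthly omnibus test to a phase contrast accounts for 79 − 43 = 36, 84 − 35 = 49 and 88 − 26 = 62 points, which is a separate matter.

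**Step 5: does a paired test cure the problem?** In the settings of Steps 1 to 3 the paired t-test rejects in 4.5–5.9%. Now add a month effect shared by the whole ward, such as a busy month, taking 2/5/10% of the variance, with one rating per month and no effect of the switch. The paired test rejects in about 13/24/39%, against 4/21/55% for one-way ANOVA by month. At 2% and 5% the paired test is the worse of the two.

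**The case against.** Several points on the other side have force.

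- *The error rate need not be wrong.* This stands. Steps 2 and 3 contain settings near 5%. A reader might infer that the test is inflated, or that its error rate certainly departs from 5%. The documents support neither, because they fix neither the grouping nor the ratings used.
- *The power loss looks larger than it is.* This stands. Setting 26–43% against 85–99% suggests a very large cost, but most of it comes from comparing an omnibus monthly test with a contrast placed exactly at the simulated step. The paired figures also rest on constant correlation: under monthly AR(1) correlation 0.3/0.5/0.7, paired power is only 62/62/67%.
- *Section 8 says analysis at professional level is descriptive.* That sentence conflicts with Table 4 but does not remove the test named there. It does support a descriptive remedy.
- *Anonymous forms may be why IWS, unlike EBPAS, has no repeated measures test.* This is possible, so the contrast between the two rows does not prove an oversight. Unlinked ratings from the same nurses are still correlated, however, so one-way ANOVA is not made valid.
- *A paired test is itself no test of the switch.* This stands, as Step 5 shows, and it limits what the fix may claim.
- *IWS is only secondary and has no success threshold.* True, and the recommendation is sized accordingly.

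**Conclusion.** The concern holds in this form: the named test assumes independence that the rating schedule rules out, so its p-value cannot be relied on, and the direction of the error is open. The illustrated range runs from about 0–1% to about 19–41%, with values near 5% in between. It rests on an assumed 20 nurses and assumed correlations, so it shows what can happen, not what will. The power cost that belongs to ignoring the pairing is about 6–11 points under constant correlation of 0.3–0.7.

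A reader might infer that the trial's success decision is affected. It is not. The SUS threshold and the 20% reduction in spot checks do not use this test. The termination rule in sections 7.c and 7.f counts the share of staff in the highest IWS category and does not use it either. This should be changed, but it does not threaten the primary evaluation.

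**What to change.** Choose one of two.

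**(a) With the forms as they stand.** In the IWS row of Table 4, replace one-way ANOVA by descriptive statistics per month, without a p-value. This agrees with the opening sentence of section 8 and costs one table entry.

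**(b) If a test is wanted.** Before data collection:

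- Add a pseudonymous nurse code to the IWS form, and align the consent wording in section 4.b and on the form in section 11.
- State whether all weekly ratings or one per month enter, and how each nurse's ratings are summarised within a phase.
- Compare phase 1 (months 1–3) with phase 2 (months 4–6, where "During phase 2 (month 4-6) patients will be monitored with the Healthdot primarily") within nurse, among nurses with ratings in both. The Wilcoxon signed-rank test is the natural choice, since Table 4 calls IWS ordinal. In the setting of Step 4 its power was 84/94/99%, close to the paired t-test.
- Report the result as a difference between two periods only. On one ward without a comparison ward, it cannot separate the switch from other ward-wide changes.

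The cost of (b) is less anonymity in a small team, a code to remember, the loss of nurses who rate in only one phase, and a pass through the amendment procedure in section 9.c. The code has to come first because no later linkage step is described.
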